**ENROLLMENT INTO RUN-IN PHASE**

**Major Eligibility Criteria at Enrollment for Run-in Phase** (see section 2.2 for a complete listing)

- Age 5 to <13 years of age at time of enrollment. Participants within 4-weeks of their 13th birthday are not eligible.
- Refractive error meeting the following by cycloplegic autorefraction:
  - Myopia -1.00D to -6.00D spherical equivalent (SE) in both eyes
  - Astigmatism <=1.50D in both eyes
  - Anisometropia <1.00D SE
- Currently wearing refractive correction
- Excellent compliance with refractive correction (>75% of waking hours) for ≥1 month prior to enrollment
- No current or previous myopia treatment with atropine, pirenzepine or other anti-muscarinic agent
- No current or previous use of bifocals, progressive-addition lenses, or multi-focal contact lenses
- No current or previous use of orthoK, rigid gas permeable, or other contact lenses to reduce myopia progression
- No known atropine allergy

**Enrollment Exam Procedures**

- Standard Refraction (with or without cycloplegia)
- Cycloplegic Autorefraction
- Cycloplegic Axial Length Measurement and Additional Biometry
- Prescribe refractive correction or change in refractive correction (if needed)
- Prescribe artificial tear eyedrops to be used one drop to each eye nightly for 2-4 weeks

**RUN-IN PHASE (2-4 WEEKS)**

- All participants are treated with daily artificial tear eyedrops
- Glasses are updated, if needed

**RANDOMIZATION VISIT (2-4 WEEKS AFTER ENROLLMENT)**

**Additional Eligibility Criteria for Randomization**

- Compliance with artificial tear eyedrops at least 90% during the run-in phase
- Excellent compliance with refractive correction (more than 75% of all waking hours) during the run-in phase
- Refractive correction in each eye (single vision eyeglasses or contact lenses with any necessary adjustment for contact lens rotation and vertex distance) that meets the following criteria:
  - Myopia (by spherical equivalent) in both eyes must be corrected to within ±0.50 D of the investigator’s cycloplegic measurement of refractive error.
  - Cylinder power in both eyes must be within ±0.50 D of the investigator’s standard refraction technique, which can be based on a cycloplegic or non-cycloplegic refraction.
  - Cylinder axis for both eyes must be within ±5 degrees of the axis found on the investigator’s refraction when cylinder power is ≥ 1.00 D or within ±15 degrees when the cylinder power is <1.00 D.
- Best-corrected distance visual acuity in current correction meeting the following criteria:
  - 20/32 or better in each eye (≥76 letters by E-ETDRS testing)
  - Interocular difference ≤ 0.2 logMAR (≤ 10 letters by E-ETDRS testing)

**Testing Procedures**

- Eye Drop Questionnaire
- Distance Visual Acuity Testing
- Binocular Near Visual Acuity
- Binocular Amplitude of Accommodation
- If > 4 weeks since enrollment into run-in phase, repeat cycloplegic autorefraction, axial length measurement and additional biometry

[figure not shown]
**IF NOT ELIGIBLE**  
withdraw  
participant from  
study

**IF ELIGIBLE**  
RANDOMIZE 2:1

**Daily 0.01% Atropine eye drops**

**Daily Placebo eye drops**

773  
774  
775  
776  
777  
778  
779

## Chapter 2: ENROLLMENT

### 2.1 Eligibility Assessment and Informed Consent/Assent

The study plans to enroll a maximum of 400 participants into the Run-In Phase for whom informed consent is provided, such that approximately 186 participants will enter the Randomized Trial Phase. The number of participants randomized who self-report as East Asian ethnicity will be limited to no more than 25% of the overall sample (n=47 participants).

As the enrollment goal into the Randomized Trial Phase approaches 186 participants, sites will be notified of the end date for recruitment into the Run-In Phase. Participants whose parents have signed an informed consent form may be entered into the Run-in Phase until the end date, which means the expected number for the Randomized Trial Phase might be exceeded during the Run-in Phase. Enrollment into the Run-In Phase may be temporarily halted if necessary until it is determined how many participants in the Run-in Phase will enter the Randomized Trial Phase. The anticipated randomized total of 186 participants could be exceeded as participants already enrolled into the Run-In Phase become eligible for the Randomized Trial Phase.

The study will be discussed with the child's parent(s) or guardian(s) (referred to subsequently as parent(s)). Parents who express an interest in the study will be given a copy of the informed consent form to read. Written informed consent / assent must be obtained from the parent and child prior to performing any study-specific procedures that are not part of routine care.

### 2.2 Eligibility Criteria for Enrollment into Run-in Phase

The following criteria must be met for the child to be enrolled into the study:

#### Inclusion Criteria

- Age 5 years to <13 years at time of enrollment. Children within 4 weeks of their 13th birthday are not eligible.
- Refractive error meeting the following by cycloplegic *autorefracton*:
  - Myopia -1.00D to -6.00D spherical equivalent (SE) in both eyes
  - Astigmatism  $\leq 1.50$ D in both eyes
  - Anisometropia <1.00D SE
- Currently wearing refractive correction (single vision eyeglasses or contact lenses)
- Excellent compliance with refractive correction (more than 75% of all waking hours) for at least one month, based on investigator judgment after discussion with parent.
- Gestational age  $\geq 32$  weeks.
- Birth weight >1500g.
- Parent understands the protocol and is willing to accept randomization to atropine or placebo.
- Is willing to participate in a 2 to 4 week run-in phase using daily artificial tear eyedrops.
- Able to return in 2 to 4 weeks for possible randomization.
- Parent has a phone (or access to phone) and is willing to be contacted by Investigator's site staff.
- Relocation outside of the area of an active PEDIG site within next 32 months is not anticipated.

#### Exclusion Criteria

- 827 • Current or previous myopia treatment with atropine, pirenzepine or other anti-muscarinic  
828 agent.
- 829 • Current or previous use of bifocals, progressive-addition lenses, or multi-focal contact  
830 lenses.
- 831 • Current or previous use of orthoK, rigid gas permeable, or other contact lenses being used  
832 to reduce myopia progression.
- 833 • Known atropine allergy.
- 834 • Abnormality of the cornea, lens, central retina, iris or ciliary body.
- 835 • Current or prior history of manifest strabismus, amblyopia, or nystagmus.
- 836 • Prior eyelid, strabismus, intraocular, or refractive surgery.
- 837 • Down syndrome or cerebral palsy.
- 838 • Diseases known to affect accommodation, vergence, or ocular motility (e.g., multiple  
839 sclerosis, Grave's disease, myasthenia gravis, diabetes mellitus, Parkinson's disease)
- 840 • Existing ocular conditions (e.g., retinal disease, cataracts, ptosis) or  
841 systemic/neurodevelopmental conditions (e.g., Down syndrome) which may influence  
842 refractive development.
- 843 • Any condition that in the judgement of the investigator could potentially influence  
844 refractive development.
- 845 • Existing conditions that may affect the long-term health of the eye or require regular  
846 pharmacologic treatment that may adversely interact with study medication (e.g., JIA,  
847 glaucoma, diabetes mellitus, pre-diabetes)
- 848 • Inability to comprehend and/or perform any study-related clinical tests
- 849 • Females who are pregnant, lactating, or intending to become pregnant within the next 30  
850 months.
  - 851 ➤ A negative urine pregnancy test will be required for all females who have  
852 experienced menarche.

### 854 **2.3 Historical Information**

855 Historical information elicited will include the following: date of birth, sex, race, ethnicity,  
856 current refractive correction, iris color (brown or not brown), parental history of myopia (0, 1, or  
857 2 parents), current medication use, history of and current medical conditions, and myopia  
858 treatment history.

### 860 **2.4 Testing at the Enrollment/Run-in Visit**

861 Testing at the enrollment visit/run-in visit will include the following:

#### 862 1. Standard Refraction

- 864 • The investigator may use his/her standard refraction technique (with or without  
865 cycloplegia) at any time during the visit to ensure that the participant meets eligibility  
866 criteria with respect to refractive correction as described in section 2.5.

#### 867 2. Cycloplegic Autorefraction

- 868 • 1% cyclopentolate – one drop twice to each eye with 5 minutes between drops. The  
869 use of proparacaine prior to the cycloplegic drops is at investigator discretion.
- 870 • Three measurements of sphere, cylinder, and axis will be obtained for each eye using  
871 autorefraction (see manual of procedures). Each measurement will be converted to a  
872 spherical equivalent refractive error (SER) and the mean of the 3 SER values for each  
873 eye will be used for confirming eligibility.

- 874
- 875
- 876
- 877
- 878
- 879
- 880
- 881
- 882
- 883
- A specific autorefractor model is not required for the study; however, each participant should have their autorefraction assessed using the same instrument during the entire study.
  - The cycloplegic autorefraction should occur at 30 minutes  $\pm$  5 minutes from the time the second drop of 1% cyclopentolate was instilled.
  - If eyes are not sufficiently dilated/cyclopleged and/or if the dilation/cycloplegia has worn off before all cycloplegic procedures have been performed, another drop of 1% cyclopentolate may be administered, followed by an additional 30-minute wait before testing. The use of proparacaine prior to this cycloplegic drop is at investigator discretion.

884 3. Axial Length Measurement and Additional Biometry

- 885
- 886
- 887
- 888
- 889
- 890
- 891
- 892
- 893
- 894
- 895
- 896
- One summary reading based on multiple measures with cycloplegia using optical biometry will be documented for the following (see procedures manual):
    - Axial length
    - Flat corneal radius
    - Anterior Chamber depth
    - Lens thickness, if available
  - A specific instrument is not required for the study; however, each participant should have axial length and additional biometry assessments made using the same instrument during the entire study.
  - If eyes are not sufficiently dilated and/or if the dilation has worn off before all cycloplegic procedures have been performed, see procedure for re-dilation in step #2.

897 **2.5 Refractive Correction**

898 To be eligible for randomization, the participant must be wearing refractive correction in each

899 eye (single vision eyeglasses or soft, daily wear single vision contact lenses with any necessary

900 adjustment for contact lens rotation and vertex distance) that meets the following criteria:

- 901
- 902
- 903
- 904
- 905
- 906
- 907
- Myopia (by spherical equivalent) in both eyes must be corrected to within  $\pm 0.50$  D the investigator's cycloplegic measurement of refractive error.
  - Cylinder power in both eyes must be within  $\pm 0.50$  D of the investigator's standard refraction technique, which can be based on a cycloplegic or non-cycloplegic refraction.
  - Cylinder axis for both eyes must be within  $\pm 5$  degrees of the axis found on the investigator's standard refraction when cylinder power is  $\geq 1.00$  D or within  $\pm 15$  degrees when the cylinder power is  $< 1.00$  D.

908 Measurement of refractive error for assessing the above criteria may be performed as an over-

909 refraction or without refractive correction.

910

911 If the participant meets all eligibility criteria for the run-in phase (see section 2.2) but their

912 current correction does not meet the requirements for randomization, then a change in refractive

913 correction can be prescribed in order to meet the requirements when the participant returns for

914 potential randomization. A change in refractive correction can also be prescribed if the

915 investigator elects to change a smaller amount of refractive error, but the resulting prescription

916 must meet the criteria above. The prescribed correction can be single vision eyeglasses or

917 contact lenses. Single vision lenses will be paid for by the study; contact lenses will be at the

918 participants' own expense. A pair of eyeglasses is recommended for all participants.

919

920 **2.6 Treatment in Run-In Phase**

921 Artificial tears will be dispensed in single-use ampules to be used 1 drop to each eye nightly in  
922 each eye for 2-4 weeks. Study personnel will demonstrate for the parent and participant how to  
923 instill a drop in each eye prior to the participant leaving the office.

924  
925 The following will be done to promote compliance with artificial tears during the run-in phase:

- 926 • A calendar log will be provided to the parent on which the participant or parent will  
927 record whether or not the installation was done each night.
- 928 • The parent and participant will be instructed to bring all unused ampules of artificial  
929 tears with them when they return in 2-4 weeks.
- 930 • A smart phone application may be offered to participants and/or parents who provide  
931 consent to be contacted with a nightly prompt asking if the eyedrops were given.

932  
933 Participants will be encouraged to wear refractive correction for all waking hours. The calendar  
934 log used to record artificial tears treatment will also be used to indicate whether refractive  
935 correction was worn each day.

936

937

## Chapter 3: RANDOMIZATION

938

939 The participant should return to assess eligibility for randomization within 2-4 weeks after using  
940 nightly artificial tears wearing the optical correction prescribed at the enrollment visit. If the  
941 participant is unable to return for possible randomization within 6 weeks of enrollment into the  
942 run-in, the participant will be withdrawn from the study.

943

### 3.1 Assessment of Compliance with Artificial Tears

944 Calendar logs will be reviewed to assess the level of compliance with artificial tears eyedrops  
945 during the run-in phase. The number of unused artificial tears eyedrop ampules will be counted.

946

947  
948 To be eligible for randomization, participants must have used artificial tear eyedrops in both eyes  
949 for at least 2 weeks and must have been at least 90% compliant with instilling the drops in both  
950 eyes (days compliant/total days since receiving study medication as evident by review of the  
951 compliance calendar and count of unused ampules) in the run-in phase. Participants not able to  
952 return both the unused ampules of artificial tears eyedrops and the calendar log, and participants  
953 returning the log who are not compliant at least 90% will be withdrawn from the study.

954

955 In addition, the parent (or participant) must demonstrate the ability to instill an eyedrop in both  
956 eyes on their own prior to being considered for randomization. Participants who can't  
957 demonstrate successful instillation of eyedrops (either by themselves or by their parent) will be  
958 withdrawn from the study.

959

### 3.2 Assessment of Compliance with Refractive Correction

960 Calendar logs will be reviewed to assess the level of compliance with refractive correction  
961 during the run-in phase. Compliance with refractive correction will be classified as excellent  
962 (76% to 100% waking hours), good (51% to 75%), fair (26% to 50%), or poor (0 to 25%) based  
963 on investigator judgment after review of the compliance calendar and discussion with parent.  
964 Participants with excellent (greater than 75% compliance) will be eligible for randomization.  
965 Participants 75% compliant or less will be withdrawn from the study.

966

### 3.3 Testing at the Randomization Visit

967  
968  
969 Participants judged to be compliant with eyedrops and refractive correction will have the  
970 following assessed:

971

#### 972 1. Eye Drop Questionnaire

- 973 • To be completed by the child prior to any other testing to evaluate effect of eye drops  
974 on the child

#### 975 2. Distance Visual Acuity Testing: Monocular distance visual acuity testing tested at the 976 start of the exam without cycloplegia in current correction meeting the requirements in 977 section 2.5.

- 978 • Measurement of best corrected visual acuity in each eye by a study certified visual  
979 acuity tester using the E-ETDRS testing protocol.

#### 980 3. Binocular Near Visual Acuity Testing: Binocular near visual acuity is measured using the 981 ATS4 Near Acuity Test with the participant wearing current refractive correction and 982 prior to administration of cycloplegia.

983 4. Binocular Amplitude of Accommodation: Measured with a study-specified and provided  
984 accommodation near-point rule (e.g. Gulden’s near-point rule) and the participant in their  
985 current spectacle or contact lens correction.  
986

987 Cycloplegic autorefraction, axial length and additional biometric assessments (following the  
988 same procedure as described for enrollment in section 2.4) must be repeated if the enrollment  
989 visit was completed more than 4 weeks (>28 days) prior to randomization. If repeated, these will  
990 be considered the participant’s “baseline” measurements; otherwise the measurements from the  
991 enrollment/run-in phase visit will be considered the “baseline” measurements.  
992

### 993 **3.4 Confirmation of Eligibility for Randomization**

994 Visual acuity testing to assess eligibility for randomization must be performed in the  
995 participant’s current refractive correction.  
996

997 Randomization will occur at the conclusion of the randomization exam after confirming that the  
998 participant meets the following eligibility criteria:  
999

- 1000 • Best-corrected distance visual acuity in current correction meeting the following criteria:
    - 1001 ○ 20/32 or better in each eye ( $\geq 76$  letters by E-ETDRS testing)
    - 1002 ○ Interocular difference  $\leq 0.2$  logMAR ( $\leq 10$  letters by E-ETDRS testing)
    - 1003
  - 1004 • Refractive error meeting the following by cycloplegic *autorefraction (only if repeated on*  
1005 *day of randomization)*:
    - 1006 ○ Myopia -1.00D to -6.00D spherical equivalent (SE) in both eyes
    - 1007 ○ Astigmatism  $\leq 1.50$ D in both eyes
    - 1008 ○ Anisometropia  $< 1.00$ D SE
    - 1009
  - 1010 • Refractive correction that is being worn for each eye (single vision eyeglasses or contact  
1011 lenses with any necessary adjustment for contact lens rotation and vertex distance) must  
1012 meet the following criteria:
    - 1013 ○ Myopia (by spherical equivalent) in both eyes must be corrected to within  $\pm 0.50$   
1014 D of the investigator’s cycloplegic measurement of refractive error.
    - 1015 ○ Cylinder power in both eyes must be within  $\pm 0.50$  D of the investigator’s standard  
1016 refraction technique, which can be based on a cycloplegic or non-cycloplegic  
1017 refraction.
    - 1018 ○ Cylinder axis for both eyes must be within  $\pm 5$  degrees of the axis found on the  
1019 investigator’s refraction when cylinder power is  $\geq 1.00$  D or within  $\pm 15$  degrees  
1020 when the cylinder power is  $< 1.00$  D.
- 1021 Measurement of refractive error for assessing the above criteria may be performed as an  
1022 over-refraction or without refractive correction.
- 1023 • Compliant with artificial tears eyedrops during run-in phase (*see definition in section 3.1*)
  - 1024 • Compliant with refractive correction during run-in phase (*see definition in section 3.2*).  
1025

1026 Participants who do not meet eligibility criteria will be withdrawn from the study without being  
1027 randomized.  
1028

1029 Prior to randomization, the study requirements should again be discussed with the parent so that  
1030 site staff have reasonable assurance that the participant will be adherent to the protocol.

1031  
1032  
1033  
1034  
1035  
1036  
1037  
1038  
1039  
1040  
1041  
1042  
1043  
1044  
1045  
1046  
1047  
1048  
1049  
1050  
1051  
1052  
1053  
1054

### **3.5 Randomization**

Eligible participants will be randomly assigned 2:1 to the atropine (0.01%) or placebo group (administering one drop nightly for 24 months), respectively, using a permuted block design stratified by iris color (brown vs non-brown) and by site. The number of participants randomized who self-report as East Asian ethnicity will be limited to no more than 25% of the overall sample (n=47 participants).

A participant is officially enrolled in the randomized trial when the website randomization process is completed.

Once a participant is randomized, that participant will be included in the analysis regardless of whether the assigned treatment is received or not. Participants will remain in the study for 30 months of follow-up. Thus, the investigator must not randomize a participant until he/she is convinced that the parent/participant remains willing to participate and will accept either of the treatment regimens and complete follow-up as previously discussed at enrollment.

Treatment must commence within 1 week following randomization; therefore, a participant should not be randomized until both the investigator and parent are ready to start treatment.

The participant, parents, coordinators, testers and investigators will be masked to treatment group. If the need arises, the investigator may become unmasked after discussion of a specific case with the protocol chair in response to any adverse events.

## Chapter 4: TREATMENT AND FOLLOW-UP IN RANDOMIZED TRIAL

### 4.1 Study Medication

Nevakar is manufacturing the study drug (0.01% atropine) and placebo and packaging both in identical-appearing single-use ampules. In addition to 0.01% atropine, the ampules contain a buffer similar to artificial tears while the placebo contains just the buffer similar to artificial tears. The atropine and placebo ampules are sent to a central pharmacy, which will label and package multiple atropine or placebo ampules into three month supply packages to maintain masking. The packages of ampules will be shipped to participating sites in insulated shipping boxes designed to maintain study drug at 59 to 77 degrees F during shipping. Participating sites will store study drug at room temperature (between 68 and 77 degrees F) prior to dispensing study medication packages to study participants. Additional study medication details are summarized within a separate investigational product manual.

### 4.2 Treatment 0 to 24 Months

Treatment with study medication will be one drop in both eyes each night, including the night before study visits. Participants who are wearing contact lenses will be instructed to remove contact lenses before administering eyedrops and wait at least 30 minutes after eyedrop administration before reinserting contact lenses.

During the first 24 months of the study, no myopia progression prevention treatment other than the study eyedrops is permitted.

### 4.3 Telephone Calls

Two weeks following randomization ( $\pm 3$  days), the site will contact parents to question the parent as to whether the child is experiencing any issues with treatment.

At three months following randomization ( $\pm 1$  month), the site will contact parents to encourage compliance and question the parent as to whether the child is experiencing any issues with treatment.

The site coordinator will make phone calls in between office visits at 9, 15, 21, and 27 months following randomization ( $\pm 1$  month). These calls will be conducted to maintain direct contact with the parents of each participant, to develop and maintain rapport with the participant and/or family, and to assist with the scheduling of study visits if needed.

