#### 1121 **4.8 Follow-up Visit Schedule in Randomized Trial**

1122 The follow-up visit schedule consists of the following office visits timed from randomization:

- 1123 • 6 months  $\pm$  2 weeks\*
- 1124 • 12 months  $\pm$  2 weeks\*
- 1125 • 18 months  $\pm$  2 weeks\*
- 1126 • 24 months  $\pm$  4 weeks: On-Treatment Primary Outcome – discontinue treatment after visit
- 1127 • 30 months  $\pm$  4 weeks: Off-Treatment Secondary Outcome – six months following  
1128 discontinuation of treatment

1129  
1130 \*A virtual visit may be completed at 6, 12, or 18-months if an in-person office visit cannot be  
1131 completed by the participant. If any safety events are identified during a virtual visit, participants will  
1132 have additional follow up as applicable.  
1133

1134 Additional visits may be scheduled at investigator discretion. Adverse event data may be reported  
1135 and collected at any time during the study.  
1136

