#### 1137 **4.9 Follow-up Visit Testing Procedures**

1138 At each office visit the following tests and assessments will be done with the participant wearing  
1139 their current refractive correction:  
1140

- 1141 1. Medical History - including questioning about the occurrence of adverse effects of treatment.  
1142 Concomitant medications will be recorded, as well as current eyeglasses or contact lenses  
1143 correction.
- 1144 2. Compliance Assessment
  - 1145 • All unused study medication ampules since the last visit (if brought to the visit) will  
1146 be counted as a measure of compliance.
  - 1147 • Home calendar logs (if brought to the visit) will be reviewed and assessments of  
1148 compliance with eyedrops and with refractive correction will be recorded on the  
1149 Follow-up Examination Form

- 1150 3. Eye Drop Questionnaire (all follow up visits except the 30-month visit)  
1151 • To be completed by the child prior to any other testing to evaluate the effect of eye  
1152 drops on the child.
- 1153 4. Distance Visual Acuity Testing (30-month visit only): Monocular distance visual acuity  
1154 tested at the start of the exam without cycloplegia in current correction.  
1155 • Measurement of best corrected visual acuity in each eye by a study certified visual  
1156 acuity tester using the E-ETDRS testing protocol.  
1157 • If the vision is more than one line ( $\geq 5$  letters) worse than baseline, retest using trial  
1158 frames or phoropter with the most recent subjective refraction.
- 1159 5. Binocular Near Visual Acuity Testing (6-month visit only): Binocular near visual acuity is  
1160 measured using the ATS4 Near Acuity Test with participant wearing current refractive  
1161 correction prior to administration of cycloplegia.
- 1162 6. Binocular Amplitude of Accommodation: Measured in their current correction without  
1163 cycloplegia with a study-specified and provided accommodation near-point rule (e.g.  
1164 Gulden's near-point rule).
- 1165 7. Standard Refraction  
1166 • The investigator may use their standard refraction technique (with or without  
1167 cycloplegia) at any time during the visit to ensure that refractive correction meets  
1168 study criteria at each visit (see section 4.9 below).  
1169 • At 30-month visit, only required if the vision is more than one line ( $\geq 5$  letters)  
1170 worse than baseline.
- 1171 8. Following cycloplegia, at all visits an examiner masked to treatment group will perform:  

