1172 • Cycloplegic Autorefraction – (see section 2.4)  
1173 • Cycloplegic Axial Length Measurement and Additional Biometry (see section 2.4)  
1174

1175 If a virtual visit is completed, only items 1 through 3 above will be completed. If any safety events  
1176 are identified during a virtual visit, participants will have additional follow up as applicable.  
1177

1178 In addition, females who have experienced menarche will undergo a urine pregnancy test at each  
1179 follow up visit except the 30-month visit (or at home if a virtual visit is completed).  
1180

- 1181 • In the case of pregnancy during the study, study eyedrops will be discontinued although  
1182 the subject will be retained in the study.  
1183

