## 1344 **6.3 Data and Safety Monitoring Committee Review of Adverse Events**

1345 A Data and Safety Monitoring Committee will approve the protocol, template informed consent  
1346 form, and substantive amendments, and provide independent monitoring of adverse events.

1347 Cumulative adverse event data will be tabulated for review by the DSMC at intervals determined  
1348 by the coordinating center and the DSMC. Following each DSMC data review, a summary will  
1349 be made available for submission to Institutional Review Boards.

1350

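### The 9-, 15- and 21-month calls carry no stated question about treatment problems, so scheduled adverse-effect enquiries on drops run 3, 1, 1, 1 per half-year and later side effects may be under-recorded in both arms

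*Protocol*

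**What the plan says.** Section 4.3 (Telephone Calls) describes three kinds of call.

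- At 2 weeks, "the site will contact parents to question the parent as to whether the child is experiencing any issues with treatment".
- At 3 months, "the site will contact parents to encourage compliance and question the parent as to whether the child is experiencing any issues with treatment".
- After that, "The site coordinator will make phone calls in between office visits at 9, 15, 21, and 27 months following randomization". The stated purpose changes: "These calls will be conducted to maintain direct contact with the parents of each participant, to develop and maintain rapport", with help in scheduling visits where needed. No question about treatment problems is mentioned.

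Section 4.8 sets visits at 6, 12, 18, 24 and 30 months; drops stop at month 24. Each visit starts with "Medical History - including questioning about the occurrence of adverse effects of treatment" (section 4.9, item 1). Virtual visits keep this item: "If a virtual visit is completed, only items 1 through 3 above will be completed". Section 4.8 also allows adverse events to be reported at any time. Section 6.1 lists the ocular and systemic effects to ask about but does not say when. Section 6.3 adds: "Cumulative adverse event data will be tabulated for review by the DSMC at intervals determined" by the coordinating center and the DSMC.

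**The concern.** The calls at 9, 15 and 21 months fall in the middle of each later half-year on drops and already put the site in touch with the parent, yet the question asked at 3 months is missing from their stated content. The effects listed in section 6.1, such as light sensitivity, near blur, irritation, and systemic effects within an hour of a drop, can be brief. A parent asked at month 12 may not mention something that came and went in month 7.

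Two things would be at stake. Absolute side-effect rates over 18 of the 24 treated months could be too low. A decline in recorded events after month 6 could also look like growing tolerance when part of it comes from asking less often. Section 7.8.1 gives the collection of more safety data on atropine as the reason for 2:1 allocation, so incomplete capture works against a stated aim of the design. Analysis cannot recover events that nobody asked about.

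**Working it through.** The protocol gives no figure for how completely side effects are captured, so there is nothing of its own to reproduce.

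**Step 1: count of scheduled enquiries on drops.** Calls with a treatment question come from 4.3 (0.5 and 3 months); visits come from 4.8 and 4.9 (6, 12, 18 and 24 months).

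- Months 0-6: 2 weeks, 3 months, 6-month visit = 3
- Months 6-12, 12-18 and 18-24: one visit each = 1, 1, 1

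The windows on the calls (±3 days and ±1 month) do not move either out of the first half-year. The gaps before an enquiry are therefore 0.5, 2.5 and 3 months early on, and 6 months each time afterwards.

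**Step 2: what the count means under a recall window.** Assumptions, not in the protocol: events are brief and occur at a constant true rate, an event is recorded only if an enquiry follows within *w* months, and nothing is reported spontaneously. The share captured is the sum of min(*w*, gap) over the gaps, divided by 6.

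- Months 0-6: [min(*w*, 0.5) + min(*w*, 2.5) + min(*w*, 3)] / 6
- Later half-years now: min(*w*, 6) / 6
- Later half-years with a mid-interval question: 2 × min(*w*, 3) / 6

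| *w* (months) | Months 0-6 | Later, now | Early-to-late ratio | Later, question added |
|---|---|---|---|---|
| 1 | 2.5/6 = 42% | 1/6 = 17% | 2.5 | 2/6 = 33% |
| 2 | 4.5/6 = 75% | 2/6 = 33% | 2.25 | 4/6 = 67% |
| 3 | 6/6 = 100% | 3/6 = 50% | 2.0 | 6/6 = 100% |
| 4 | 100% | 4/6 = 67% | 1.5 | 100% |
| 6 | 100% | 100% | 1.0 | 100% |

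**Step 3: the same check with gradual forgetting.** Suppose instead that the chance of recall halves every *h* months, again an assumption. Mean recall over a gap *L* is (1 − e^(−kL)) / (kL), with k = ln 2 / *h*. For *h* = 3:

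- Gaps of 0.5, 2.5 and 3 months give 0.944, 0.760 and 0.721. Weighted by length: (0.5 × 0.944 + 2.5 × 0.760 + 3 × 0.721) / 6 = 0.756.
- A 6-month gap gives 0.541, so the apparent fall is 1 − 0.541/0.756 = 28%.
- With the question added, later capture is 0.721 and the apparent fall is 1 − 0.721/0.756 = 5%.
- Capture over 24 months goes from (0.756 + 3 × 0.541)/4 = 0.595 to (0.756 + 3 × 0.721)/4 = 0.730, a gain of 23%.

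| *h* (months) | Months 0-6 | Later, now | Apparent fall | Later, question added | Fall then | Gain over 24 months |
|---|---|---|---|---|---|---|
| 1.5 | 0.592 | 0.338 | 43% | 0.541 | 9% | 38% |
| 3 | 0.756 | 0.541 | 28% | 0.721 | 5% | 23% |
| 6 | 0.865 | 0.721 | 17% | 0.845 | 2% | 12% |

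At *h* = 12 the present fall is only about 9% (0.929 against 0.845).

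**Step 4: what the change does to the count.** Adding the question at 9, 15 and 21 months gives 3, 2, 2, 2. The longest gap drops from 6 to 3 months, but the first half-year keeps one extra enquiry.

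**The case against.** A reader might infer that recorded rates must fall with time on drops because of the schedule alone. The protocol does not support that. Each visit question, virtual visits included, can reach back over the whole preceding interval, and with 6-month recall the early-to-late ratio is 1.0. Effects that persist while drops continue would still be present at the next visit. The percentages above depend on recall parameters that appear nowhere in the protocol and set spontaneous reporting to zero.

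Other objections also stand:

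- The eye drop questionnaire is given at randomization and at 6, 12, 18 and 24 months, with no telephone part. It is summarized at each visit, and its 24-month item average is the named test (7.4.1). Call content cannot affect it.
- Both masked arms follow the same schedule, so it does not favour either arm.
- The protocol names no analysis of adverse events by period; section 6.3 only tabulates them cumulatively.
- It is tempting to add that adherence support stops at 3 months. Section 4.5 says otherwise: calendars, ampule counts, an interview at each visit, and encouragement of noncompliant families without a time limit.
- It is also tempting to say that a problem after month 6 necessarily stays unknown until the next visit. Parents can raise it on a call, additional visits are allowed (4.8), and serious or unexpected events have their own immediate reporting route (6.2).

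Front-loading can be defended too. Table 2 in section 1.7 cites a retrospective series of seven children on 0.01% atropine in which reading difficulty arose in the first weeks and did not last beyond 4-6 weeks. That is a good reason to ask early, but not a reason to leave the question off later calls. The provision for reporting at any time allows a report but prompts nobody. Coordinators may ask anyway, but practice could then differ between sites.

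Finally, section 4.3 does not say that answers on the early calls are recorded as adverse events. This weakens the count somewhat, and is also a reason to state how answers are recorded.

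**Conclusion.** The point holds as a low-severity matter of safety ascertainment. The count of 3, 1, 1, 1 follows directly from sections 4.3, 4.8 and 4.9. The consequence is conditional: if recall of short-lived effects is shorter than 6 months, later effects are under-recorded in both arms, and part of any fall in recorded adverse events may reflect less frequent questioning. Under the assumed recall windows, the early-to-late capture ratio runs from 2.5 (1 month) to 1.0 (6 months). Under gradual forgetting with half-lives of 1.5 to 6 months, the apparent fall runs from 43% to 17%. These figures illustrate the mechanism and do not estimate what happened in this trial.

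The comparison between arms is not biased, and the questionnaire, the primary analysis and the sample size are unaffected. The case for acting is that the calls already take place and the trial chose its allocation ratio to gain safety data.

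**What to change.** In section 4.3, have the 9-, 15- and 21-month calls ask the same treatment-problem question as the 3-month call, and state that any answers are recorded as adverse events under 6.1 with an onset date. Because the schedule would then be 3, 2, 2, 2, any description of adverse events over time should note the denser questioning in months 0-6. The 27-month call falls after drops have stopped and is not needed for this purpose.

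The cost is one sentence in 4.3, a short script on calls already made, a few more forms, and slightly higher recorded side-effect counts in both arms.
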